#### **7.1.2.6.2 End of Treatment and Follow-up Tumor Imaging**

In participants who discontinue study treatment, tumor imaging should be performed at the time of treatment discontinuation ( $\pm 4$ -week window). If previous imaging was obtained within 4 weeks prior to the date of discontinuation, then imaging at treatment discontinuation is not mandatory. In participants who discontinue study treatment due to documented disease progression and the Investigator elects not to implement iRECIST, this is the final required tumor imaging.

In participants who discontinue study treatment without documented disease progression, every effort should be made to continue monitoring their disease status by tumor imaging using the same imaging schedule used while on treatment.

#### **7.1.2.6.3 RECIST 1.1 Assessment of Disease**

RECIST 1.1 will be used as the primary measure for assessment of tumor response, date of disease progression, and as a basis for all protocol guidelines related to disease status (e.g., discontinuation of study treatment). Although RECIST 1.1 references a maximum of 5 target lesions in total and 2 per organ, the Sponsor allows a maximum of 10 target lesions in total and 5 per organ, if clinically relevant to enable a broader sampling of tumor burden.

#### **7.1.2.6.4 iRECIST Assessment of Disease**

iRECIST is based on RECIST 1.1, but adapted to account for the unique tumor response seen with immunotherapeutic drugs. When clinically stable, participants should not be discontinued until progression is confirmed by the Investigator, working with local radiology, according to the rules below. This allowance to continue treatment despite initial radiologic PD takes into account the observation that some participants can have a transient tumor flare in the first few months after the start of immunotherapy, and then experience subsequent disease response.

[figure not shown]
A description of the adaptations and iRECIST process is provided in the Appendix, with additional detail in the iRECIST publication[47]. iRECIST will be used by the Investigator to assess tumor response and progression, and make treatment decisions.

## Imaging and Treatment after First Radiologic Evidence of Progressive Disease

	Clinically Stable		Clinically Unstable	
	Imaging	Treatment	Imaging	Treatment
First radiologic evidence of PD by RECIST 1.1	Repeat imaging at 4 to 8 weeks to confirm PD.	May continue study treatment at the Investigator's discretion while awaiting confirmatory tumor imaging by site by iRECIST.	Repeat imaging at 4 to 8 weeks to confirm PD per Investigator's discretion only.	Discontinue treatment
Repeat tumor imaging confirms PD (iCPD) by iRECIST per Investigator assessment	No additional imaging required.	Discontinue treatment (exception is possible upon consultation with Sponsor).	No additional imaging required.	Not applicable
Repeat tumor imaging shows iUPD by iRECIST per Investigator assessment	Repeat imaging at 4 to 8 weeks to confirm PD. May occur at next regularly scheduled imaging visit.	Continue study treatment at the Investigator's discretion.	Repeat imaging at 4 to 8 weeks to confirm PD per Investigator's discretion only.	Discontinue treatment
Repeat tumor imaging shows iSD, iPR, or iCR by iRECIST per Investigator assessment.	Continue regularly scheduled imaging assessments.	Continue study treatment at the Investigator's discretion.	Continue regularly scheduled imaging assessments.	May restart study treatment if condition has improved and/or clinically stable per Investigator's discretion. Next tumor image should occur according to the regular imaging schedule.

iCPD = iRECIST confirmed progressive disease; iCR = iRECIST complete response; iRECIST = modified Response Evaluation Criteria in Solid Tumors 1.1 for immune-based therapeutics; iSD = iRECIST stable disease; iUPD = iRECIST unconfirmed progressive disease; PD = progressive disease; RECIST 1.1 = Response Evaluation Criteria in Solid Tumors 1.1.

## Imaging and Treatment for Clinically Stable Participants after First Radiologic Evidence of PD Assessed by the Investigator

### 7.1.3 Other Procedures

#### 7.1.3.1 Withdrawal/Discontinuation

When a participant discontinues/withdraws prior to trial completion, all applicable activities scheduled for the final trial visit should be performed at the time of discontinuation. Any adverse events which are present at the time of discontinuation/withdrawal should be followed in accordance with the safety requirements outlined in Section 7.2 - Assessing and Recording Adverse Events.

#### 7.1.4 Visit Requirements

Visit requirements are outlined in the Trial Flow Chart. Specific procedure-related details are provided above in Section 7.1 - Trial Procedures.

## 7.1.5 Post-treatment Visits

### 7.1.5.1 Safety Follow-Up Visit

The mandatory Safety Follow-Up Visit should be conducted approximately 30 days after the last dose of study treatment or before the initiation of a new anti-cancer treatment, whichever comes first. All AEs that occur prior to the Safety Follow-Up Visit should be recorded. Participants with an AE of Grade > 1 will be followed until the resolution of the AE to Grade 0-1 or until the beginning of a new anti-cancer therapy, whichever occurs first. SAEs that occur within 90 days of the end of treatment or before initiation of a new anti-cancer treatment should also be followed and recorded.

### 7.1.5.2 Follow-up Visits

Participants who discontinue study treatment for a reason other than disease progression will move into the Follow-Up Phase and should be assessed every 12 weeks ( $84 \pm 7$  days) by radiologic imaging to monitor disease status. Every effort should be made to collect information regarding disease status. Information regarding post-study anti-cancer treatment will be collected if new treatment is initiated.

### 7.1.5.3 Survival Follow-up

Participants who experience confirmed disease progression or start a new anticancer therapy, will move into the Survival Follow-Up Phase and should be contacted by telephone every 12 weeks to assess for survival status until death, withdrawal of consent, or the end of the trial, whichever occurs first.

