#### **7.1.1.5.3 Subsequent Anti-Cancer Therapy Status**

The investigator or qualified designee will review all new anti-neoplastic therapy initiated after the last dose of trial treatment. If a participant initiates a new anti-cancer therapy within 30 days after the last dose of trial treatment, the 30-day Safety Follow-up visit must occur before the first dose of the new therapy. Once new anti-cancer therapy has been initiated the participant will move into survival follow-up.

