### 7.1.2.6 Tumor Imaging and Assessment of Disease

Except where PET/CT is indicated based on the Study Flow Chart, computed tomography (CT) is the preferred tumor imaging. For the abdomen and pelvis, contrast-enhanced magnetic resonance imaging (MRI) may be used when CT with iodinated contrast is contraindicated, or when local practice mandates it. MRI is the strongly preferred modality for imaging the brain. The same imaging technique regarding modality, ideally the same scanner, and the use of contrast should be used in a participant throughout the study to optimize the reproducibility of the assessment of existing and new tumor burden and improve the accuracy of the assessment of response or progression based on imaging.

Brain imaging is required for all participants at screening. MRI is preferred; however, CT imaging will be acceptable, if MRI is medically contraindicated.

Participant eligibility will be determined using local assessment (Investigator assessment) based on RECIST 1.1. In addition, images (including via other modalities) that are obtained at an unscheduled time point to determine disease progression, as well as imaging obtained for other reasons, but which demonstrate radiologic progression, should also be used to determine progression.

When the Investigator identifies radiographic progression per RECIST 1.1, efforts should be made to verify radiologic PD. Treatment should continue until PD has been verified. Regardless of whether PD is verified, if the Investigator considers the participant has progressed, but elects to implement iRECIST, the Investigator will assess for confirmation of progression by iRECIST at subsequent time points.

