#### **7.1.2.6.1 Tumor Imaging During the Study**

On-study imaging assessments should be performed at the timepoints ( $\pm 7$  days) detailed in the Trial Flow Chart for each study cohort. Imaging timing should follow calendar days and should not be adjusted for delays in cycle starts. Imaging should continue to be performed until disease progression is identified by the Investigator. Once disease progression is confirmed, imaging should be performed as needed for routine clinical care and does not need to adhere to the Trial Flow Chart.

Per iRECIST (Section 9.2.1.6), disease progression should be confirmed by the site 4 to 8 weeks after first radiologic evidence of PD in clinically stable participants. Participants who have unconfirmed disease progression may continue on treatment at the discretion of the Investigator until progression is confirmed by the site provided they have met the conditions detailed in Section 9.2.1.6. Participants who receive confirmatory imaging do not need to undergo the next scheduled tumor imaging if it is less than 4 weeks later; tumor imaging may resume at the subsequent scheduled imaging time point, if clinically stable. Participants who

have confirmed disease progression by iRECIST, as assessed by the site, will discontinue study treatment. Exceptions are detailed in Section 9.2.1.6.

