## 8.0 STATISTICAL ANALYSIS PLAN

### 8.1 Statistical Analysis Plan – Primary Endpoint and Sample Size Calculation

The **primary endpoint** is progression-free survival (PFS) in the PembroRT cohort one year following study enrollment. PFS duration will be defined as the time from study registration to the date of disease progression or death from any cause. In cases where a scan is concerning for progressive disease based on RECIST 1.1 criteria, and progression is confirmed on a subsequent scan 4-8 weeks later (satisfying iRECIST criteria for progression), the date of disease progression would be the date of the first scan demonstrating progression. PFS rates will be estimated using the Kaplan-Meier Survival method, from which the probability of PFS at various time points and corresponding 95% confidence intervals will be estimated. If a patient is lost to follow-up without having disease progression, progression-free survival will be censored at the date of the patient's last clinic visit. Based on published multi-institutional trials and data from our institution, we expect the one-year progression-free survival rate ( $H_0$ ) to be to 40% with standard chemoradiotherapy. We hypothesize that this rate will be at least 65% ( $H_1$ ) for subjects in the PembroRT cohort. A one sample two-sided log-rank test will be used to compare the one-year PFS rate in the PembroRT cohort against the expected rate with ChemoRT. We plan to accrue **25 subjects to the PembroRT cohort**. Assuming that the accrual period will last 18 months and that event rates will follow an exponential distribution, this sample size will provide 81% power to detect an improvement in PFS at 1 year at a 5% level of significance using a one sample two-sided log-rank test [48, 49].

The ChemoRT cohort will be open to accrual while accrual to the PembroRT cohort is ongoing. We expect that approximately 40% of patients with locally advanced NSCLC have PD-L1 expression of at least 50%. We therefore expect that approximately 38 subjects will be enrolled and treated with standard concurrent chemoradiotherapy as part of this trial, which will yield a **total sample size of approximately 63 subjects**.

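### Patients who start a new anticancer therapy before progression are sent to telephone-only survival follow-up, which contradicts the imaging-until-progression rules and leaves PFS after a switch undefined

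*Combined protocol and SAP*

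**What the plan says.** Two sections move a patient to survival follow-up because of new therapy alone. Section 7.1.5.3 covers patients who have confirmed progression "or start a new anticancer therapy, will move into the Survival Follow-Up Phase and should be contacted by telephone every 12 weeks"; the contact is for survival status. Section 7.1.1.5.3 says: "Once new anti-cancer therapy has been initiated the participant will move into survival follow-up".

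Three sections point the other way for a patient without progression:
- Section 7.1.2.6.1 (Tumor Imaging During the Study): "Imaging should continue to be performed until disease progression is identified by the Investigator".
- Section 7.1.2.6.2, for patients who stop study treatment without documented progression: "every effort should be made to continue monitoring their disease status by tumor imaging using the same imaging schedule used while on treatment". It also asks for a scan at treatment discontinuation, within 4 weeks either side.
- Section 7.1.5.2: "Participants who discontinue study treatment for a reason other than disease progression will move into the Follow-Up Phase", with imaging every 12 weeks. For that same phase it adds: "Information regarding post-study anti-cancer treatment will be collected if new treatment is initiated".

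Section 7.1.2.6 adds that "imaging obtained for other reasons, but which demonstrate radiologic progression, should also be used to determine progression".

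Section 8.1 defines PFS as registration to progression or death from any cause. Its one censoring rule is: "If a patient is lost to follow-up without having disease progression, progression-free survival will be censored at the date of" the last clinic visit. New anticancer therapy is not mentioned.

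**The concern.** The primary endpoint depends on finding progression, yet one pair of sections replaces scans with telephone calls while the patient may still be progression-free. Four sites enrol (Section 5.7), and each could reasonably follow a different reading.

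The PembroRT cohort, which carries the primary endpoint, is exposed. Table 3 and Section 5.5 provide for stopping pembrolizumab for reasons other than progression, and Section 5.4.2 places no restriction on therapies in post-treatment follow-up. A patient who switches and is then telephoned is not lost to follow-up, so the rule in 8.1 does not apply. The analyst would have to choose, with the data in hand, between running the patient event-free to death, censoring, and using whatever scans exist. With 25 patients, a fixed 40% benchmark and no randomised control, one or two such choices matter. Freedom from distant metastasis and from intrathoracic progression (Section 8.2) have the same gap.

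**Working it through.** **1. The plan's own figure.** Inputs from 8.1: n = 25, one-year PFS 40% against 65%, exponential times, 18 months' accrual, one-sample two-sided log-rank test at 5%. Follow-up after the last enrolment is not stated there; I assume 12 months.

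- Hazards: -ln 0.40 = 0.916 and -ln 0.65 = 0.431 per year; ratio 0.470.
- Expected events under 65%: 25 × [1 - (e^(-0.431) - e^(-0.431×2.5)) / (0.431×1.5)] = 13.0.
- Expected events at the null hazard over the same follow-up: 13.0 / 0.470 = 27.7.
- Z = (O - E)/√E is centred at (13.0 - 27.7)/√27.7 = -2.79. With the exact variance under 65%, power is 80.6%, against the stated 81%. Simulation gives 83.1%.

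The power figure is therefore not in dispute, though it needs about 12 months' follow-up (10 months gives 78.2%, 6 months 71.0%).

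**2. A simple bound.** If a share q of events is censored just before it happens, one-year PFS S appears as S^(1-q):

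| q | true 40% | true 65% |
|---|---|---|
| 5% | 0.40^0.95 = 41.9% | 66.4% |
| 10% | 0.40^0.90 = 43.8% | 67.9% |
| 20% | 0.40^0.80 = 48.0% | 70.8% |

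This treats deaths as lost too, so it overstates the problem: telephone contact captures deaths.

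**3. Simulation that keeps deaths.** Assumptions, none from the documents: 15% of PFS events are deaths; median one year from progression to death; a share q of progressors switch two months before progression (only where progression falls later than two months after registration). Expected switchers by one year at q = 20%: 25 × 0.85 × 0.20 × (e^(-0.916×2/12) - e^(-0.916×14/12)) = 2.2; at 5% and 10%, about 0.5 and 1.1. True one-year PFS is 40%; with no switching, the favourable-tail error is 1.6%.

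| q | censored at switch: one-year PFS; error | only death counted: one-year PFS; error |
|---|---|---|
| 5% | 41.2%; 2.5% | 41.4%; 2.5% |
| 10% | 42.3%; 3.3% | 42.9%; 4.3% |
| 20% | 44.7%; 5.9% | 45.7%; 8.6% |

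**4. Does the direction hold under other switching patterns?** True 40% again:

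| Pattern | 5% | 10% | 20% |
|---|---|---|---|
| Unrelated to risk, censored at switch | 40.0% | 40.0% | 40.1% |
| Unrelated to risk, only death counted | 40.8% | 41.8% | 43.5% |
| Low-risk patients switch, censored at switch | 39.2% | 38.3% | 36.8% |

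For the first two rows the percentage is the share switching by one year. In the low-risk rows about 0.5, 1.0 and 2.0 of 25 patients switch by one year. The sign depends on who switches and on how switchers are handled.

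**The case against.** The strongest reply is that nothing in the protocol says imaging stops at new therapy. Sections 7.1.2.6.1, 7.1.2.6.2 and 7.1.5.2 continue it, scans taken for other reasons count, and the scan at discontinuation should catch many patients who switch because they are worsening. This stands. A reader might infer that the protocol ends ascertainment of progression for switchers; the documents support only a contradiction. It does not remove the problem: 7.1.1.5.3 and 7.1.5.3 are the only places that assign a follow-up phase because of new therapy, and counting incidental scans schedules none.

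A reader might also infer that PFS is necessarily inflated. It is not: step 4 shows no bias or a downward bias under plausible patterns. Nor does 8.1 direct that switchers be censored at the last clinic visit; that rule is for patients lost to follow-up.

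A larger effect is tempting, such as the 48.0% in step 2. It rests on an assumed 20% rate and on censoring every affected event, deaths included, immediately before it occurs.

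Finally, one might argue that ChemoRT patients lose imaging when adjuvant therapy starts. Section 5.2.2 and the flow chart provide for adjuvant therapy within that cohort, so calling it new anticancer therapy is a strained reading. A clarifying sentence is enough.

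**Conclusion.** The contradiction is certain from the text, and so is the silence of 8.1 on new therapy before progression. The consequence is conditional. If sites follow the telephone rule, and if switching anticipates progression or switchers are counted event-free until death, PFS in the PembroRT cohort is overstated. With about 0.5 to 2.2 informative switches by one year among 25 patients, the overstatement is roughly 1 to 6 percentage points at a true 40%. These sizes rest on the assumed switch rates, the two-month lead, the 15% share of deaths and 12 months' follow-up; the actual switch rate is unknown. This should be corrected because it touches the primary endpoint and there is no concurrent randomised arm to share the error. It does not undermine the sample size.

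**What to change.** In 7.1.1.5.3 and 7.1.5.3, limit telephone-only follow-up to patients with documented progression, and say that the imaging already specified in 7.1.2.6.1 (Tumor Imaging During the Study), 7.1.2.6.2 and 7.1.5.2 continues until progression whether or not a new therapy has started. Add one sentence that adjuvant therapy allowed in the ChemoRT cohort is not new anticancer therapy for this purpose. In 8.1, state that PFS is analysed regardless of new therapy, which is what its definition already implies, and add censoring at new therapy as a sensitivity analysis. Apply the same rule to the two freedom-from-progression endpoints in 8.2.

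The cost is protocol wording and scans that the protocol already calls for elsewhere. Sample size and power are unchanged. Some patients will be harder to image after switching.

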## 7.2 Assessing and Recording Adverse Events

An adverse event is defined as any untoward medical occurrence in a patient or clinical investigation participant administered a pharmaceutical product and which does not necessarily have to have a causal relationship with this treatment. An adverse event can therefore be any unfavorable and unintended sign (including an abnormal laboratory finding, for example), symptom, or disease temporally associated with the use of a medicinal product or protocol-specified procedure, whether or not considered related to the medicinal product or protocol-specified procedure. Any worsening (i.e., any clinically significant adverse change in frequency and/or intensity) of a preexisting condition that is temporally associated with the use of the Merck's product, is also an adverse event.

Merck product includes any pharmaceutical product, biological product, device, diagnostic agent or protocol-specified procedure, whether investigational (including placebo or active comparator medication) or marketed, manufactured by, licensed by, provided by or distributed by Merck for human use.

Adverse events may occur during the course of the use of Merck product in clinical trials, or as prescribed in clinical practice, from overdose (whether accidental or intentional), from abuse and from withdrawal.

All AEs, SAEs and other reportable safety events that occur after the consent form is signed but before treatment allocation/randomization must be reported by the investigator if the participant is receiving placebo run-in or other run-in treatment, if the event causes the participant to be excluded from the study, or is the result of a protocol-specified intervention, including but not limited to washout or discontinuation of usual therapy, diet, or a procedure.

- All AEs from the time of treatment allocation/randomization through 30 days following cessation of study treatment must be reported by the investigator.
- All AEs meeting serious criteria, from the time of treatment allocation/randomization through 90 days following cessation of study treatment, or 30 days following cessation of study treatment if the participant initiates new anticancer therapy, whichever is earlier must be reported by the investigator.
- All pregnancies and exposure during breastfeeding, from the time of treatment allocation/randomization through 120 days (pembroRT cohort) or 180 days (chemoRT cohort) following cessation of study treatment, or 30 days following cessation of study treatment if the participant initiates new anticancer therapy must be reported by the investigator.
- Additionally, any SAE brought to the attention of an investigator at any time outside of the time period specified above must be reported immediately by the investigator if the event is considered to be drug-related.

Investigators are not obligated to actively seek AE or SAE or other reportable safety events in former study participants. However, if the investigator learns of any SAE, including a death, at any time after a participant has been discharged from the study, and he/she considers the event to be reasonably related to the study treatment or study participation, the investigator must promptly notify Merck.

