For the purpose of data collection, all untoward events that occur after informed consent through 90 days after the last dose of study drug must be recorded on the subject’s CRF by the investigational site. This requirement includes AEs from unscheduled as well as scheduled visits. The investigator is responsible for ensuring that all AEs and SAEs that are observed or reported during the study are recorded on appropriate CRFs and reported in accordance with protocol instructions. The study period during which all AEs must be

reported begins after informed consent is obtained and study treatment is initiated and ends 90 days after last administration of study treatment, or at the time of initiation of another anti-cancer therapy, whichever occurs first. AEs and SAEs that are observed or reported prior to initiation of study treatment should be recorded on appropriate CRFs if they are associated with protocol-mandated interventions (e.g., invasive procedures such as biopsies).

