## 7.1.2 Clinical Procedures/Assessments

### 7.1.2.1 Adverse Event (AE) Monitoring

The investigator or qualified designee will assess each participant to evaluate for potential new or worsening AEs as specified in the Trial Flow Chart and more frequently if clinically indicated. Adverse experiences will be graded and recorded throughout the study and during the follow-up period according to NCI CTCAE Version 4.0 (see Appendix). Toxicities will be characterized in terms regarding seriousness, causality, toxicity grading, and action taken with regard to trial treatment.

Please refer to section 7.2 for detailed information regarding the assessment and recording of AEs.

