### **7.2.3 Immediate Reporting of Adverse Events to the Sponsor and to Merck**

#### **7.2.3.1 Serious Adverse Events**

A serious adverse event is any adverse event occurring at any dose or during any use of Merck's product that:

- Results in death;
- Is life threatening;
- Results in persistent or significant disability/incapacity;
- Results in or prolongs an existing inpatient hospitalization;
- Is a congenital anomaly/birth defect;
- Is another important medical event

• **Note:** In addition to the above criteria, adverse events meeting either of the below criteria, although not serious per ICH definition, are reportable to the Merck in the

same timeframe as SAEs to meet certain local requirements. Therefore, these events are considered serious by Merck for collection purposes.

- Is a new cancer (that is not a condition of the study);
- Is associated with an overdose.

Refer to Table 7 for additional details regarding each of the above criteria.

For the time period beginning when the consent form is signed until treatment allocation/randomization, any serious adverse event, or follow up to a serious adverse event, including death due to any cause that occurs to any participant must be reported within 24 hours to the Sponsor and within 2 working days to Merck Global Safety if it causes the participant to be excluded from the trial, or is the result of a protocol-specified intervention, including but not limited to washout or discontinuation of usual therapy, diet, placebo treatment or a procedure.

For the time period beginning at treatment allocation through 90 days following cessation of treatment, or 30 days following cessation of treatment if the participant initiates new anticancer therapy, whichever is earlier, any serious adverse event, or follow up to a serious adverse event, including death due to any cause whether or not related to the Merck product, must be reported within 24 hours to the Sponsor and within 2 working days to Merck Global Safety.

Additionally, any serious adverse event, considered by an investigator who is a qualified physician to be related to Merck product that is brought to the attention of the investigator at any time following consent through the end of the specified safety follow-up period specified in the paragraph above, or at any time outside of the time period specified in the previous paragraph also must be reported immediately to Merck Global Safety.

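### Non-serious adverse events have contradictory collection end dates, and section 8.2 compares the cohorts on them without a common window, so over unequal periods

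*Combined protocol and SAP*

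**What the plan says.** Four sections of the protocol say how long non-serious adverse events are collected.

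- Section 7.2: "All AEs from the time of treatment allocation/randomization through 30 days following cessation of study treatment must be reported by the investigator".
- Section 7.1.5.1 sets a visit about 30 days after the last dose, or before new anti-cancer treatment if that comes first: "All AEs that occur prior to the Safety Follow-Up Visit should be recorded". Events already present are not dropped: "Participants with an AE of Grade > 1 will be followed until the resolution of the AE to Grade 0-1", or until new therapy.
- Section 5.7, on data collection: "all untoward events that occur after informed consent through 90 days after the last dose of study drug must be recorded". Two sentences later it says that the period in which all adverse events must be reported "ends 90 days after last administration of study treatment, or at the time of initiation of another anti-cancer therapy, whichever occurs first".
- Section 7.1.2.1: "Adverse experiences will be graded and recorded throughout the study and during the follow-up period according to NCI CTCAE Version 4.0". It gives no length and refers to 7.2 for detail.

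Serious events have their own rule in 7.2, a limit of 90 days once therapy has stopped: "or 30 days following cessation of study treatment if the participant initiates new anticancer therapy, whichever is earlier must be reported by the investigator". Section 7.2.3.1 makes them reportable irrespective of cause, "including death due to any cause whether or not related to the Merck product, must be reported within 24 hours to the Sponsor".

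Section 4.6.2.2 names grade ≥3 adverse events and grade ≥2 pneumonitis as safety endpoints, without a time window. Section 8.2 presents adverse event rates as counts and percentages and compares the cohorts by chi-square or Fisher exact test. It gives no window, common time point or exposure adjustment.

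**The concern.** There are two linked problems. First, a site cannot tell from the text when collection of non-serious events ends. The lead site and the three subsites could follow different sections, each with a basis in the protocol. Second, the numeric windows are all tied to the end of study treatment, and the two regimens differ greatly in length. A crude proportion then mixes the risk of an event with the time during which it could be recorded.

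This bears on secondary objectives 5 and 6: fewer severe adverse events with PembroRT, and no significant increase in pneumonitis. If PembroRT patients are observed longer, PembroRT can look worse when the true risks are equal. The events most exposed are new non-serious grade ≥2 pneumonitis, which is not an event of clinical interest in 7.2.3.2, and non-serious grade ≥3 events. Section 5.2.3 places radiographic radiation change in the lung typically within six months of treatment, and a 30-day ChemoRT window would miss most of that period. The later contacts in 7.1.5.2 and 7.1.5.3 name imaging, disease status, new treatment and survival, but not adverse events.

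**Working it through.** **Inputs**
- PembroRT: 15 doses (5.5); three induction cycles (3.2, objective 4) every three weeks; maintenance visits in weeks 18 to 51 (6.0).
- ChemoRT: 20–37 fractions (5.2.3); optional adjuvant therapy (5.2.2); a flow-chart footnote gives a start 4–6 weeks after radiotherapy.
- Windows: 30 days = 30/7 = 4.3 weeks; 90 days = 90/7 = 12.9 weeks.
- Assumptions: five fractions per week; PembroRT radiotherapy ends before week 18; the adjuvant footnote applies to whichever adjuvant drug is used. The flow chart is not fully legible, so these cannot be confirmed.

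**The plan's own figures**
- Doses: 3 + [(51 − 18)/3 + 1] = 3 + 12 = 15, as in 5.5.
- ChemoRT size: 25/0.40 × 0.60 = 37.5, the stated 38.

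**End of all-event collection, in weeks from start of treatment**

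| Patient | 30-day rule (7.2) | 90-day rule (5.7) |
|---|---|---|
| PembroRT completer | 51 + 4.3 = 55.3 | 51 + 12.9 = 63.9 |
| ChemoRT, 20 fractions, no adjuvant | 4.0 + 4.3 = 8.3 | 4.0 + 12.9 = 16.9 |
| ChemoRT, 37 fractions, no adjuvant | 7.4 + 4.3 = 11.7 | 7.4 + 12.9 = 20.3 |
| Difference | 43.6 to 47.0 | 43.6 to 47.0 |

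The difference is the same under both rules, because it equals 51 minus the length of chemoradiotherapy. Settling on 30 or 90 days removes the contradiction but leaves the inequality.

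**Coverage after radiotherapy**
- ChemoRT without adjuvant therapy: 30/183 = 16% of the first six months under 7.2, or 90/183 = 49% under 5.7.
- PembroRT completer: at least (51 − 18) + 4.3 = 37.3 weeks, so the whole six months (26.1 weeks).

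**Effect of how adjuvant therapy is classed** (one year of it, the duration mentioned in 4.6)
- As study treatment, 30-day rule: 4 + 52 + 4.3 = 60.3 to 6 + 52 + 4.3 = 62.3 weeks after radiotherapy. From start of treatment this is 4.0 + 60.3 = 64.3 to 7.4 + 62.3 = 69.7 weeks, later than the 55.3 for PembroRT.
- As another anti-cancer therapy: the second 5.7 rule closes collection 4–6 weeks after radiotherapy.

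**Does a 12-month common window suffice?** Twelve months is 52.2 weeks. Six months after radiotherapy falls at or before 18 + 26.1 = week 44.1 in PembroRT. In ChemoRT it falls at 4.0 + 26.1 = 30.1 to 7.4 + 26.1 = 33.5. Both lie inside the window.

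**Weight of one patient:** 1/38 = 2.6 percentage points in ChemoRT; 1/25 = 4.0 in PembroRT.

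**The case against.** The strongest reply has five parts.

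- **A site can satisfy both rules by recording to 90 days.** Section 7.2 sets a minimum for reporting, and 5.7 governs the case report form that feeds the analysis. This would be a good answer if 5.7 spoke only of recording. It also says that all events must be reported to 90 days, so the sections still disagree.
- **Counting events over the regimen plus a tail is a common safety summary.** Extra events in a longer regimen are partly real toxicity. This stands, and such rates should be kept. They do not by themselves support a statement that one regimen carries more or less risk over the same time.
- **Adjuvant therapy is probably study treatment.** Section 5.2.2 falls under the heading for study treatments, and 5.4.2 prohibits only therapy that the protocol does not specify. This stands. A reader might infer that 5.7 closes ChemoRT collection 4–6 weeks after radiotherapy; that is the weaker reading, although the protocol is not explicit.
- **The largest contrast is an extreme.** It sets PembroRT completers against ChemoRT patients without adjuvant therapy. At the hypothesised 65% one-year PFS, only about 0.65 × 25 = 16 PembroRT patients would be progression-free at one year, and toxicity would stop some of those. Section 4.6 also says that adjuvant immunotherapy has changed the standard of care for many such patients. This stands.
- **The consequence is limited.** The comparisons are exploratory and allocation is by PD-L1. The ChemoRT toxicity row of the flow chart ends in a visit marked X+ at an unreadable week, which may recover some events. This also stands.

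**Conclusion.** The point holds as two findings. The wording conflict is certain: about 30 days in 7.2 and 7.1.5.1 against 90 days in 5.7, with no rule of precedence. The unequal observation is a separate matter. It follows from tying the window to the end of treatment and from 8.2 setting no common window. At its widest it is about 44–47 weeks, under the scheduling assumptions above. It is smaller for PembroRT patients who stop early, and it can shrink or reverse for ChemoRT patients whose adjuvant therapy counts as study treatment.

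Three stronger readings are not supported.

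- A reader might infer that the 30/90-day conflict causes the inequality. It does not, because the difference is identical under both rules.
- A reader might infer that serious toxicity goes uncounted. Serious events are reportable to 90 days, or to 30 if new therapy starts, and many grade ≥3 events will be serious through hospitalization. Their window also runs from the end of treatment, so it is unequal too, but the coverage is better.
- A reader might infer a large, known bias against PembroRT. Suppose both cohorts share a true six-month pneumonitis risk of 10–40%, the hazard is constant, every event is non-serious, PembroRT is seen for all six months and ChemoRT for only 30 days after radiotherapy. The Fisher test would then reject in 16–86% of trials, against 2.6–3.6% with a common six-month window. None of those conditions comes from the documents, so the figures illustrate a mechanism only. The number of missed events cannot be estimated, and the direction depends on adjuvant use and how it is classed.

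The PFS analysis is unaffected. The correction is worth making because it is cheap and the comparison of safety profiles is one of the stated reasons for the ChemoRT cohort.

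**What to change.** 1. Align 5.7, 7.1.2.1, 7.1.5.1 and 7.2 so that all adverse events are collected to 90 days after the last study treatment. Leave expedited reporting as it is.
2. State whether ChemoRT adjuvant therapy under 5.2.2 is study treatment or new anti-cancer therapy for the purpose of this window.
3. In both cohorts, record every grade ≥2 pneumonitis and every grade ≥3 event from registration to 12 months, whatever its seriousness. Use clinic visits, imaging visits and record review, with telephone contacts only as a prompt.
4. In 8.2, compare the cohorts over that common window and give the number of patients observed to its end. Add a sensitivity analysis that censors at new therapy given for progression; onset dates are already recorded under Table 7.
5. Keep the regimen-plus-tail rates, and late immune events after month 12, as a descriptive summary.

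The cost is a short amendment and a few case report form fields. Reported toxicity rates will be slightly higher, and some events will be hard to attribute. The common window ends about one week after the last scheduled pembrolizumab dose (52.2 − 51 = 1.2 weeks), so late immune events, which 5.2.1.2 says can arise months after the last dose, fall outside the formal comparison.
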